A skin sample was taken following the standard procedure described for the diagnosis of mycosis (5). The epithelial surface was disinfected with 70° alcohol and a sample was collected from the affected area by scalpel scraping. Subsequently, the sample was analyzed using two different procedures. The 30% KOH test (35.3g/100ml distilled water) (Labbox, Barcelona, Spain) followed by conventional light microscopy observation to identify the infective fungal agent, and microbiological culture on Sabouraud dextrose agar with chloramphenicol and cycloheximide (Condalab, Torrejón de Ardoz, Madrid), at a constant temperature (between 25°C and 28°C) for 2 to 4 weeks, in order to inhibit molds and bacteria and observe the growth of the infective fungal agent. Participants with infection were considered to be those who had positive results in both tests, excluding cases in which only one test was positive.

- Bacteriological culture

A skin sample was taken following the standardized procedure for microbiological analysis (6). The skin was disinfected with 70° alcohol and a sample was taken by smear with a sterile swab from the affected surface. Again, the analysis was carried out using two distinct and independent procedures. A Gram stain was performed to identify bacteria and the sample was inoculated with Sabouraud dextrose broth (SDA) (Merck, Germany), at a constant temperature (between 27°C and 31°C) for 1 to 3 days. Participants with infection were considered to be those who had positive results in both tests, excluding cases in which only one test was positive.

Variables and statistical analysis

The following variables were analyzed: sociodemographic (sex and age), anthropometric (weight, height, and BMI), hygiene-related habits (frequency of foot washing, use of flip-flops in showers/pools, type of footwear and socks and frequency of sock change), presence or absence and type of infection, degree of hydration and concentration of EC group T0 (0%), group T1 (1%) and group T2 (0.5%). Of these variables, age, weight, height, BMI, and hydration were considered quantitative compared to the rest that were analyzed as qualitative.

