Statistical analysis was performed using the statistical analysis program IBM-SPSS Statistics for Windows version 25 (IBM Corp. Armonk, NY, USA). Some figures have been obtained using the Python programming language, using the Seaborn library (Waskom, M. L., (2021). Seaborn: statistical data visualization. *Journal of Open-Source Software*, 6(60), 3021, <https://doi.org/10.21105/joss.03021>).

Normality was assessed using the Shapiro-Wilk test. To evaluate the influence of different variables on infection remission, a Cox regression model was used, and survival curves of significant factors were plotted. To compare the efficacy of different EC concentrations, survival curves were compared using the Log-rank test. The Mann-Whitney U test was used to assess hydration averages according to sex. To check if there were improvements in hydration due to the use of the cream with different concentrations of EC (T1 and T2) compared to the control group (T0), hydration levels were compared using Kruskal-Wallis tests, using the Mann-Whitney U test with correction of p-values by the Bonferroni method for multiple comparisons.

In all statistical tests, significance was considered when p-value<0.05 and high significance when p-value<0.01.

2. Results

Analysis of the Elemental Composition of Commercial S. S.

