Of the participants who developed skin infections, 23 were women and 9 were men. The prevalence of skin infections by sex is shown in Table 3.

Table 3. Prevalence of infections as a function of sex.

Sex	Infections			Total
	Fungal	Bacterial	Mixed	
Women	3 (9.3%)	13 (40.6%)	7 (21.8%)	23 (71.7%)
Men	1 (3.1%)	6 (18.8%)	2 (6.4%)	9 (28.3%)
Total	4 (12.4%)	19 (59.4%)	9 (28.2%)	32 (100%)

%: Percentage.

The colorations observed with Wood's light in the interdigital spaces were coral red and opaque blue (Figure 3). The coral-red coloration corresponds to a superficial bacterial infection of the skin caused by *C. minutissimum*, known as erythrasma, and the dull blue coloration corresponds to a fungal infection caused by the dermatophyte *Trichophyton schoenleinii*.

[figure not shown]

Figure 3. Fluorescence of different color emitted by pathogens under Wood's light in interdigital spaces of the feet. (A and B) erythrasma with coral-red coloration (*) and (B) suspected *Trichophyton schoenleinii* with bluish coloration (↑).

Mycological cultures were used to determine the causative agents of fungal infections. The dermatophytes and yeasts that were identified were: *Trichophyton schoenleinii*, *Trichophyton verrucosum*, *Trichophyton tonsurans* and *Candida albicans*. On the other hand, the following bacteria were identified in bacterial cultures: *Corinebacterium minutissimum*, *staphylococcus haemolyticus*, *staphylococcus epidermidis*, *staphylococcus lugdunensis*, *micrococcus luteus* and *micrococcus sp.*

Efficacy of treatments

To test whether the EC-enriched cream was effective against fungal infections, the cumulative survival curves of the two treatments, T1 and T2, were plotted (Figure 4). 100% of fungal infections resolved within 30 days with both treatments, although the EC curve at 1% was higher than 0.5%.

[figure not shown]

Figure 4. Cumulative survival curves as a function of the two treatments for fungal infections.

In fact, the mean time to achieve remission in the T1 group (1%) was 11.61 days, compared to 14.00 days in the T2 group (Table 4). However, according to the Log-rank test, the differences between the two groups were not statistically significant (p -value=0.611). Therefore, both concentrations have similar efficacy in terms of the time required to achieve remission of infection.

Table 4. Mean and median survival time (in days) of remission of fungal infection for the two EC concentrations.

Group	Media				Median			

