Variable	B (coef.)	Exp(B)	IC 95%		p-value
			Lim. Inf.	Lim. Sup	
Stature	-0.02	0.98	0.73	1.30	0.874
Weight	0.01	1.01	0.73	1.40	0.948
BMI	-0.04	0.96	0.39	2.40	0.938
Age	0.03	1.03	0.54	1.97	0.918
Sex	-0.64	0.52	0.20	1.35	0.181

Coef: coefficient; Exp: exponent; B: correlation coefficient; CI, confidence interval; Lim. Inf: lower bound; Lim. Sup: upper limit; *: statistically significant.

[figure not shown]
Regarding the possible relationship between anthropometric and sociodemographic variables and the efficacy of treatment for bacterial infections, it was observed that only sex showed a statistically significant relationship (p-value=0.028) (Table 9).

Table 9. Cox model for different anthropometric and sociodemographic variables and bacterial infection.

Variable	B (coef.)	Exp(B)	IC 95%		p-value
			Lim. Inf.	Lim. Sup	
Stature	0.11	1.12	0.82	1.54	0.484
Weight	-0.08	0.93	0.64	1.34	0.684
BMI	0.13	1.14	0.41	3.21	0.803
Age	0.55	1.74	0.82	3.67	0.146
Sex	1.41*	4.11	1.16	14.50	0.028*

Coef: coefficient; Exp: exponent; B: correlation coefficient; CI, confidence interval; Lim. Inf: lower bound; Lim. Sup: upper limit; *: statistically significant.

To assess the efficacy of the treatment over time according to sex, a cumulative survival curve was used (Figure 6) and the proportion of individuals in whom the resolution of the infection over time was observed was represented, observing that the healing time was shorter in women than in men and, therefore, a faster resolution of bacterial infection is observed in women.

**Figure 6.** Cumulative survival curve as a function of sex.

Finally, in relation to skin hydration, significant differences were obtained according to sex (p-value ≤ 0.010), with women having higher hydration averages (Table 10).

Table 10. Results of the Kruskal-Wallis tests for the analysis of hydration according to sex.

Landmarks per foot	Sex	Initial		15 days		30 days		45 days		60 days	
		Media±Sd	p-value								
Dorsal R	Woman	34.507±9.834	0.146	41.904±13.322	0.511	44.364±13.907	0.439	42.674±13.989	0.408	43.871±16.218	0.171
	Man	29.306±9.159		40.966±18.823		44.358±21.589		37.933±10.723		36.837±12.851	
Digital Plant R	Woman	29.453±11.772	0.115	39.738±16.234	0.075	37.465±14.911	0.044*	36.737±15.137	0.048*	45.303±18.070	0.015*
	Man	23.450±10.769		31.391±12.869		27.967±16.632		28.604±10.934		24.685±11.913	
Inner Arc R	Woman	28.401±19.944	0.221	32.539±22.396	0.541	31.884±20.830	0.318	29.654±18.746	0.318	30.272±18.633	0.480

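### The 1% v 0.5% bacterial comparison is not adjusted for sex, the Cox model for sex omits concentration, and sex by arm is not reported, so each estimate may be partly distorted by the other

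*Combined protocol and SAP*

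**What the plan says.** Under *Variables and statistical analysis*, two separate analyses of remission are set out. For the concentrations: "To compare the efficacy of different EC concentrations, survival curves were compared using the Log-rank test". No strata or covariates are named. For other factors: "To evaluate the influence of different variables on infection remission, a Cox regression model was used". The covariates are not listed there, although the same section counts concentration and type of infection among the variables analysed.

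In the Results, *Efficacy of treatments* gives mean times to bacterial remission of 49.35 days (1%, T1) and 44.82 days (0.5%, T2), with log-rank p=0.130. It nevertheless calls T2 the better treatment. Table 9 is titled "Cox model for different anthropometric and sociodemographic variables and bacterial infection". Its rows are stature, weight, BMI, age and sex, and the text reports that "only sex showed a statistically significant relationship (p-value=0.028"). With Figure 6, the text concludes that bacterial infection clears sooner in women.

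Of the infected, "23 were women and 9 were men". The randomisation section puts 23 infected participants in T1, 9 in T2 and none in T0. It mentions no stratification by sex. Table 1 splits the sample by origin, age group and sex, but not by arm.

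**The concern.** T0 held no infected participants, so T1 v T2 is the only between-arm comparison of remission. It is small, and it is read directionally despite p=0.130. The same data are then said to show a fourfold effect of sex. If women were unevenly spread over the two arms, part of the apparent concentration difference could come from sex, or a real difference could be partly hidden. Conversely, part of the sex effect could come from concentration. Neither analysis conditions on the other factor, and the cross-table that would settle the matter is absent.

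**Working it through.** **Reproducing Table 9.** SE = [ln(14.50) − ln(1.16)] / (2 × 1.96) = 0.644. z = ln(4.11) / 0.644 = 2.19, two-sided p = 0.028, as printed. The text says women resolve faster, so 4.11 is taken as women relative to men. Tables 8 and 9 hold ten tests: 0.028 × 5 = 0.14 and 0.028 × 10 = 0.28.

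**Analysis set.** Table 3 gives 13 + 7 = 20 women and 6 + 2 = 8 men with bacterial or mixed infection, 28 in all. Four of the 32 infected had fungal infection only, in unstated arms, so T2 held between 9 − 4 = 5 and 9 of the 28. (Table 6 counts only 20 bacterial infections, so the set is itself unclear.)

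**Concentration effect implied by p=0.130.** Here z = 1.514. With d events and a = T2's share of the 28, HR ≈ exp(1.514 / √(d·a·(1 − a))). Events are not reported, so 8 to 14 is assumed. The inverse-variance formula for sex gives roughly 1 / (0.644² × 8/28 × 20/28) ≈ 12.

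| T2 | 8 events | 12 events | 14 events |
|---|---|---|---|
| 5 | 4.05 | 3.13 | 2.88 |
| 9 | 3.15 | 2.55 | 2.38 |

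**Sex effect only (HR 4.11, no concentration effect).** With m men among T2's n, the apparent T2/T1 hazard ratio is the ratio of average hazards: {[m + 4.11(n − m)]/n} ÷ {[(8 − m) + 4.11(20 − n + m)]/(28 − n)}.

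| T2 (n) | No men in T2 | Chance of that | One SD fewer men | One SD more men |
|---|---|---|---|---|
| 5 | 1.36 | 15.8% | 1.23 | 0.79 |
| 7 | 1.41 | 6.5% | 1.20 | 0.82 |
| 9 | 1.47 | 2.4% | 1.19 | 0.83 |

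Chances and SDs are hypergeometric. The opposite extreme, as many men as possible in T2, gives 0.24 to 0.33; its probability is under 0.1% even at n = 5.

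**Effect on the test.** Adjusted z ≈ 1.514 − ln(factor) × √(d·a·(1 − a)). A one-SD imbalance moves z to between 1.21 and 1.29, or to between 1.76 and 1.85. Neither reaches 1.96. Reaching it needs a masking factor of about 0.66 to 0.77. In whole people that is at least 3 men in T2 at n = 5 (factor 0.65; chance 0.108 + 0.014 + 0.001 = 12%) or at least 5 at n = 9 (factor 0.66; chance 0.039 + 0.005 = 4%).

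**Concentration effect only (T2 all women).** Apparent sex HR = (n·c + 20 − n) / 20. For c = 2 to 3 this is 1.25 to 1.90. Reaching 4.11 needs c = (4.11 × 20 − (20 − n)) / n, which is 7.9 at n = 9 and 13.4 at n = 5.

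**Simulation of the worst case** (no men in T2, cultures at days 30 and 60, 45% remission assumed). A sex effect alone gave a median apparent T2/T1 HR of 1.63 to 1.76. With T2 = 9 it gave a log-rank z of at least 1.51 in favour of T2 in 24% of trials, against 7% with no effects at all.

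**Difference in means (Table 5).** 49.35 − 44.82 = 4.53 days; SE = √(2.38² + 4.38²) = 4.98; 95% CI −5.2 to 14.3.

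**The case against.** Assignment is described as random. If T1 v T2 was randomised, the unadjusted log-rank test is valid, and adjustment offers only precision and protection against chance imbalance. That stands, with a caveat: a control arm without a single infected participant, when 32 of 49 were infected, is hard to square with simple random allocation.

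Sex is also a weakly established factor: one of ten uncorrected tests, with an interval from 1.16 to 14.50. Adjusting for it because it was significant in the same data is a choice made after the fact. This stands too. It is equally a reason to re-estimate sex alongside concentration before relying on the claim about women.

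Finally, the report already calls the concentration difference non-significant, and a one-SD imbalance would leave it so. That is correct, but the text still draws a direction from it.

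A reader might go further and infer that each effect could simply be the other in disguise, or that an ordinary imbalance could carry the log-rank result across the significance threshold. The figures support neither. The most extreme split yields 1.36 to 1.47 (1.63 to 1.76 simulated) against an implied 2.4 to 4.1. A concentration HR of 2 to 3 cannot generate a sex HR of 4.11.

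**Conclusion.** The concern holds in limited form. The concentration test ignores sex, the sex model ignores concentration, and sex by arm is not shown, so partial distortion of each estimate by chance imbalance cannot be excluded. A one-SD imbalance shifts the T2/T1 hazard ratio by about 20% either way. Sex imbalance together with chance could produce p=0.130, but as point estimates neither effect accounts for the other.

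This is not a demonstrated bias. The sizes assume that the sex HR is truly 4.11, that Table 3's 28 are the analysis set, that T2 held 5 to 9 of them, and that there were 8 to 14 events. The adjusted estimates cannot be computed from what is reported.

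**What to change.** - State the bacterial analysis set, reconciling Tables 3 and 6. Tabulate sex, infection type and number of remissions by arm.
- Keep the unadjusted log-rank test. Beside it, report either a log-rank test stratified by sex or a Cox model with concentration and sex only. Give the T2/T1 and sex hazard ratios with 95% CIs; a stratified test alone does not supply the sex ratio.
- Do not add infection type or retain all five Table 9 covariates: about 12 events is roughly two per covariate.
- Label the adjusted analysis post hoc.
- Qualify the statements that T2 was better and that women resolve faster according to these results.

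The cost is one re-run on data already held and one small table. The downside is a wider, less stable interval, since there are at most 8 men in the set. If the table shows the arms balanced on sex, confounding by sex can largely be set aside.

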After reviewing the available literature, the essential oil (EO) of *M. alternifolia* was chosen for its antibacterial and antifungal characteristics (16–19). There were 3 types of commercial *M. alternifolia* EO from the brands Marnys® (Cartagena, Spain), Naissance® (Neath, United Kingdom) and Esencias Lozano® (Murcia, Spain). However, the choice of the specific commercial EO depended on the results obtained from the analysis of its composition. This analysis was performed using gas chromatography mass spectrometry (CG-MS) and the results obtained were contrasted with those available in the online database SpectraBase (WILEY, John Wiley & Sons).

The cream used as a base for the incorporation of the different concentrations of EO tested was a hand and nail cream (*La Chinata*®, Plasencia, Spain), in which Extra Virgin Olive Oil is used. This cream was chosen after verifying that none of its components were allergens for the skin of the participants according to Regulation 1223/2009(1). In addition, it was the treatment received by patients in the T0 group, in whom no type of EC was added.

To test the possible efficacy of the chosen *M. alternifolia* EO as a treatment against infections, the base cream was enriched with different concentrations of EO. Specifically, 1% for the T1 treatment group

and 0.5% for the T2 treatment group. The emulsion of the EO and the base cream was carried out by means of a magnetic stirrer (Agimatic-N, Barcelona, Spain) under sterile conditions (laminar flow cabinet, Telstar AV-100), adding the necessary volume of EC until the desired two concentrations were achieved.

Treatments were administered to participants in the form of prefilled 15ml syringes under sterile conditions with enough for 15 days of treatment. Along with the treatment, all the necessary information was provided on the hygienic habits to follow (washing the feet properly with soap and water and drying them properly with a towel for exclusive use), the correct way of applying the treatment, the daily volume of treatment for each foot (0.5ml/2 times a day).

Exploration, sampling, and diagnostic tests

Sociodemographic data (age and sex), medical and podiatric history, allergies and pharmacological treatments prescribed, as well as hygiene habits, were obtained through the completion of a Google Forms survey (Annex 2).

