	East.	Err. East	IC 95%		East.	Err. East	IC 95%	
			Lim. Inf.	Lim. Sup.			Lim. Inf.	Lim. Sup.
Treatment 1%	11.61	2.68	6.36	16.86	-	-	-	-
Treatment 0.5%	14.00	4.04	6.09	21.91	-	-	-	-

Est: statistical survival test; Err. Est: statistician error; CI, confidence interval; Lim. Inf: lower bound; Lim. Sup: upper limit; "-": data not available.

Similarly, to evaluate whether the EO-enriched cream was effective against bacterial infections, the cumulative survival curves for both treatments were plotted (Figure 5). In this case, the treatment curve at 0.5% concentration showed better results than the 1% treatment curve.

[figure not shown]

Figure 5. Cumulative survival curves as a function of the two treatments for bacterial infections.

Thus, the mean time to achieve remission in the T1 group (1%) was 49.35 days, compared to 44.82 days in the T2 group (0.5%) (Table 5). This indicated that the treatment of the T2 group was better, since the infection remitted 5 days earlier on average, although when comparing both treatments using the Long-rank test, no statistically significant differences were found (p -value=0.130). Median survival was 60.00 days for treatment at 0.5%, so half of the participants in the T2 group achieved remission at the end of the study. This value could not be computed for the 1% treatment, indicating that less than half of the subjects in this group experienced resolution of the infection at the end of the trial (Table 5).

Table 5. Mean and mediansurvival time (in days) of remission of bacterial infection for the two EC concentrations.

Group	Media				Median			
	East.	Err. east.	IC 95%		East.	Err. east.	IC 95%	
			Lim. Inf.	Lim. Sup.			Lim. Inf.	Lim. Sup.
Treatment 1%	49.35	2.38	44.68	54.01	-	-	-	-
Treatment 0.5%	44.82	4.38	36.2	53.40	60.0	6.37	47.51	72.49

Est: statistical survival test; Err. Est: statistician error; CI, confidence interval; Lim. Inf: lower bound; Lim. Sup: upper limit; "-": data not available.

Relationship between infections and the rest of the variables analyzed

In relation to hygiene habits, it was found that most of the participants washed their feet daily, used flip-flops in swimming pools or showers, wore breathable footwear and cotton socks, and changed their socks daily (Table 6), although it is true that these habits did not show a statistically significant relationship with respect to the presence or absence of skin infections ($p\text{-value} \geq 0.103$) (Table 7).

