Although descriptively variations in skin hydration are observed depending on the treatment applied, only the area of the "Outer Arch" of the right p-ie showed significant differences between groups, both at one and a half months of treatment ($p\text{-value}=0.028$) where the T1 group presented a lower hydration, and at its completion ($p\text{-value}=0.002$), with the T2 group having the lowest hydration (Table 1-1). After the pairwise comparison, statistically significant differences were obtained between the T0 and T1 groups at one and a half months ($p\text{-value}=0.016$), observing that the control group had greater hydration, and between the T0 and T1 groups ($p\text{-value}=0.021$) and the T0 and T2 groups ($p\text{-value}=0.003$) at the end of treatment where, as in the month and a half, the control group had greater hydration (Table 1-2).

Table 11. Results of the Kruskal-Wallis tests for the analysis of hydration as a function of time and treatment applied.

Landmarks per foot	G	Clinical Evaluation							
		Initial		15 days		30 days		45 days	
		Media±Sd	p-value	Media±Sd	p-value	Media±Sd	p-value	Media±Sd	p-value
Dorsal R	G. T0	35,506±9,364		46,356±17,565		47,787±18,500		41,144±12,744	47,612±19,149
	G. T1	32,481±9,077	0.600	39,537±14,093	0.405	42,690±16,888	0.669	40,626±13,840	0.775
	G. T2	32,095±12,123		41,366±13,255		43,522±11,821		43,332±13,482	41,433±17,052
Digital Plant R	G. T0	29,630±8,215		38,992±17,156		44,454±18,161		38,044±17,682	36,998±18,832
	G. T1	26,538±13,104	0.592	37,230±17,615	0.943	32,939±14,430	0.059	32,126±14,095	0.474
	G. T2	28,846±12,171		36,666±10,250		29,616±12,832		36,225±11,886	27,466±13,514
Inner Arc R	G. T0	31,117±15,186		31,721±18,640		35,890±23,178		32,205±18,994	37,761±17,694
	G. T1	28,705±22,666	0.135	33,491±24,892	0.687	29,179±18,094	0.457	28,441±20,519	0.633
	G. T2	17,731±9,006		25,278±12,703		25,831±17,795		24,487±9,525	21,633±11,244
External Arc R	G. T0	20,622±9,449		24,434±14,194		27,500±13,395		29,243±12,342	27,668±9,032
	G. T1	19,081±10,643	0.336	24,125±15,356	0.701	24,190±14,910	0.317	18,564±12,384	0.028*
	G. T2	15,119±8,104		20,323±14,354		19,487±11,907		20,989±11,010	13,874±7,691
Heel R	G. T0	14,873±9,495		19,435±13,382		28,527±20,929		21,406±16,765	17,062±7,272
	G. T1	14,966±14,056	0.654	21,629±19,017	0.778	19,897±13,953	0.212	17,934±15,610	0.898
	G. T2	11,102±5,294		15,928±10,798		16,457±12,132		15,501±6,685	11,152±6,825

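### No deciding endpoint is named, and two non-significant dose comparisons are read by different rules: neither similarity for fungal remission nor superiority of 0.5% for bacterial remission is shown

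*Combined protocol and SAP*

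**What the plan says.** The aim is given under *Choice of EO, base cream, and preparation of treatments*: "To test the possible efficacy of the chosen *M. alternifolia* EO as a treatment against infections", with 1% for T1 and 0.5% for T2.

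Under *Variables and statistical analysis*, the dose comparison is one sentence: "To compare the efficacy of different EC concentrations, survival curves were compared using the Log-rank test". One threshold rule covers everything: "In all statistical tests, significance was considered when p-value<0.05 and high significance when p-value<0.01". The only multiplicity correction is attached to the pairwise hydration comparisons: "using the Mann-Whitney U test with correction of p-values by the Bonferroni method for multiple comparisons". The text available names no primary endpoint, order of testing, division of alpha or exploratory label.

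Under *Efficacy of treatments* the log-rank test is run twice, T1 against T2:

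- **Fungal (Table 4):** "the mean time to achieve remission in the T1 group (1%) was 11.61 days, compared to 14.00 days in the T2 group", p=0.611. The text concludes that the two doses perform alike on time to remission.
- **Bacterial (Table 5):** means of 49.35 days (T1) and 44.82 days (T2), p=0.130. The text concludes: "This indicated that the treatment of the T2 group was better", citing remission about 5 days earlier, and then adds that the log-rank test found no significant difference.

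**The concern.** Both log-rank tests fail the document's own criterion, yet one result is turned into a statement of similarity and the other into a statement of superiority. These are different claims that need different evidence. Superiority needs an interval that excludes zero. Similarity needs an interval that lies inside a stated margin, and no margin is given. Because no endpoint or contrast was named as decisive, nothing in the plan fixes how the two results should be read, separately or together.

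At stake is the dose conclusion. A reader of the results would take away that the doses are interchangeable for fungal infection and that 0.5% is preferable for bacterial infection. The data establish neither.

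**Working it through.** **Inputs.** Means and standard errors (SE) from Tables 4 and 5; log-rank p-values from *Efficacy of treatments*; infected participants per arm (T1 23, T2 9, T0 none) from *Randomization, masking, and experimental design*; infection types (4 fungal only, 19 bacterial only, 9 mixed) from *Test results for microbiological diagnostics*.

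**1. Reproduce the printed intervals** as mean ± 1.96 × SE:

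| | Mean | SE | Recomputed | Printed |
|---|---|---|---|---|
| Fungal T1 | 11.61 | 2.68 | 6.36 to 16.86 | 6.36 to 16.86 |
| Fungal T2 | 14.00 | 4.04 | 6.08 to 21.92 | 6.09 to 21.91 |
| Bacterial T1 | 49.35 | 2.38 | 44.69 to 54.01 | 44.68 to 54.01 |
| Bacterial T2 | 44.82 | 4.38 | 36.24 to 53.40 | 36.2 to 53.40 |

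They agree within rounding, so the SEs can be used.

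**2. Difference between doses**, T1 minus T2, with SE = √(SE₁² + SE₂²):

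- Fungal: 11.61 − 14.00 = −2.39 days; SE = √(2.68² + 4.04²) = 4.85; 95% CI −11.9 to 7.1.
- Bacterial: 49.35 − 44.82 = +4.53 days; SE = √(2.38² + 4.38²) = 4.98; 95% CI −5.2 to 14.3.

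The point estimates have opposite signs and both intervals include zero. The fungal interval is compatible with 1% being faster by up to 11.9 days, which is 11.9/14.00 = 85% of the T2 mean, or slower by up to 7.1 days (51%). That is not evidence of similarity. The bacterial interval allows either dose to be the faster.

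A normal test on these mean differences gives p=0.62 and p=0.36. The bacterial log-rank p is smaller (0.130) because that test compares whole curves, but it is still not significant.

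**3. Error rate of two unadjusted tests at 0.05.**

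- Independent: 1 − 0.95² = 9.75%. Upper bound: 0.05 + 0.05 = 10%.
- Shared patients: 4 + 9 = 13 fungal and 19 + 9 = 28 bacterial, 9 in both, which limits the correlation to about 9/√(13 × 28) = 0.47. At 0.47 the rate is 9.2%.
- At an assumed correlation of 0.8 the rate is 7.8%.
- Simulated log-rank tests with these patient numbers, a 23:9 split and assumed remission times gave 8.3 to 8.6%, because the 13-patient fungal test ran at about 3.5%.

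**4. Holm adjustment of the printed p-values.** Bacterial: 2 × 0.130 = 0.26. Fungal: 0.611. No result changes.

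**The case against.** The strongest reply is that the document already reports both comparisons as non-significant, and in the bacterial case does so in the very sentence that calls T2 better. That is true, and it means that no false positive was declared. But the qualifier does not rescue the claim: the sentence asserts superiority and then reports a test that does not support it. The fungal sentence has the converse fault, since non-significance is read as similarity. The bacterial text also notes that the median was reached only in T2. The log-rank test compares those same curves and gives p=0.130.

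Second, fungal and bacterial infection are different conditions, and separate conclusions for each are defensible. This stands. Treating them as one Holm family is a matter of judgement, and it changes nothing here. The fault lies in the content of the two conclusions, not in there being two.

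Third, naming a primary endpoint now would restore no error control, because the results are known. This also stands, and the fix does not ask for it.

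A reader might go further and infer that any of the three arms could be presented as best: 1% on fungal remission, 0.5% on bacterial remission and 0% on hydration, where the text says "the control group had greater hydration". The documents do not support that. T0 contained no infected participants, so it enters neither remission comparison. The hydration difference was significant at only one of ten sites, the right external arch, on days 45 and 60. Hydration is also reported outside the efficacy section.

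**Conclusion.** The point holds for the dose conclusions. With differences of −2.39 days (about −11.9 to 7.1) and +4.53 days (about −5.2 to 14.3), the trial shows neither that the doses are similar against fungal infection nor that 0.5% is better against bacterial infection. The supported statement for both is that no difference was shown.

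The missing primary endpoint and the unadjusted tests should be disclosed, with a nominal family-wise rate of up to about 10%, roughly 8 to 10% depending on correlation and small-sample behaviour. A reader might infer that this inflation produced a false efficacy finding. It did not, because neither test was significant.

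Assumptions: the printed means and SEs are taken at face value, the arms are independent, and a normal approximation is used although T2 had at most nine infected participants. The fungal means both lie below the first post-baseline review at day 15, and the documents do not explain how those times were built, so the fungal interval inherits that uncertainty. The overlap calculation uses the 13 and 28 implied by the diagnostic results; Table 6 counts 8 fungal and 20 bacterial infections. The correlation between the tests is not given and is varied above.

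**What to change.** In *Efficacy of treatments*:

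- Delete the clause calling T2 better for bacterial infection, and the sentence calling the two concentrations similarly effective for fungal infection.
- For each endpoint, state that no difference between 1% and 0.5% was shown, with the difference in mean time, its 95% CI and the log-rank p-value.
- Add that the observed directions were opposite.

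In *Variables and statistical analysis*:

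- State that no primary endpoint was prespecified.
- State that the two remission comparisons are unadjusted, with a nominal family-wise error of up to about 10%.
- Label the hydration, sex, anthropometric and hygiene analyses exploratory.
- Holm-adjusted p-values (0.26 and 0.611) may be added as supplementary information.

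This costs wording only and needs no new data. The separate statements of superiority and similarity are lost. No significant efficacy result is lost, because there is none.
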